#### 8.3.5 ADVERSE EVENT REPORTING

Adverse event reporting will be refined with input from the DSMB during its initial meeting, to address any specific concerns related to this study protocol.

Site-based PIs will report any Unanticipated Problem Involving Risk to Subjects or Others (UPIRSO)s or AEs to the overall PI and Project Manager in a timely manner. When a UPIRSO or AE is present, the overall PI and Project Manager will submit a report to the UNC IRB within 3 working days of receipt of this information. Generally, the report should contain the following:

- Detailed information about the event or issue, including relevant dates. The report should identify the affected subjects by their study codes and not by their names or other personal identifiers.
- An assessment of whether any subjects or others were placed at risk or suffered any harm (e.g., physical, social, financial, legal or psychological) as a result of the event.
- If the event involves noncompliance, describe the result of the root cause analysis.
- Any corrective and preventative actions, planned or already taken.
- Any other information requested by OHRE, if applicable.
- If the report cannot be completed in its entirety within the required time period, the report should describe what information is still needed and when the investigator anticipates that a follow-up report will be submitted.

Information previously unknown to the IRB that suggests new or increased risk to subjects or others (hereinafter referred to as New Safety Information) is promptly reportable to OHRE within 7 calendar days of the investigator becoming aware of the information.

- Information for which the sponsor requires reporting to the IRB, may be summarized and submitted to the IRB at continuing review.
- Protocol deviations that did not harm subject(s) or others or place subject(s) or others at increased risk must be summarized and reported to the IRB at continuing review.
- Researchers may consult with the OHRE Compliance Manager if they are uncertain about what information is reportable.

### 8.3.6 SERIOUS ADVERSE EVENT REPORTING

The reporting of any AE / SAE will be based on NIA and UNC IRB standards, on the severity of the AE, its level of attribution to the intervention, and whether or not it is anticipated.

- All **adverse events that are both serious (SAE) and unexpected** would be reported to IRB, DSMB / SO, and NIA PO **within 48 hours** of the study's knowledge of SAE.
- Summary of SAEs would be reported to NIA PO and to the DSMB / PO **quarterly**, unless otherwise requested by the DSMB or a Safety Officer.
- Summary of all AEs regardless of classification would be presented for each DSMB meeting at 6-month intervals

## 8.4 UNANTICIPATED PROBLEMS

### 8.4.1 DEFINITION OF UNANTICIPATED PROBLEMS

This protocol uses the definition of Unanticipated Problems as defined by the UNC Office of Human Research Ethics (OHRE).

Unanticipated Problems are defined as

- Unexpected in terms of nature, severity, or frequency given (a) the research procedures that are described in the protocol-related documents, such as the Institutional Review

Board (IRB)-approved research protocol and informed consent document; and (b) the characteristics of the participant population being studied;

- Related or possibly related to participation in the research (“possibly related” means there is a reasonable possibility that the incident, experience, or outcome may have been caused by the procedures involved in the research); and
- Suggests that the research places participants or others at a greater risk of harm (including physical, psychological, economic, or social harm) than was previously known or recognized
- UPIRSO - Unanticipated Problem Involving Risk to Subjects or Others is any incident, experience, or outcome that:
  - is unexpected (in terms of nature, severity, or frequency) given (a) the research procedures that are described in the protocol-related documents, such as the IRB-approved research protocol and informed consent document; and (b) the characteristics of the participant population being studied;
  - is related or possibly related to a participant’s participation in the research; and
  - is serious or suggests that the research places participants or others at a greater risk of harm (including physical, psychological, economic, or social harm) than was previously known or recognized.

## 9 STATISTICAL CONSIDERATIONS

### 9.1 STATISTICAL HYPOTHESES

**Aim 1:** To conduct a multi-site RCT of the ADRD-PC program (**intervention arm**) vs publicly available educational material for dementia caregivers (**control arm**) to compare 60-day hospital transfers (hospitalization and emergency room visits) for persons with late-stage ADRD (**primary outcome**). **H1:** *60-day hospital transfers will be lower in the intervention vs. control arm.*

**Aim 2:** To compare patient-centered secondary outcomes between intervention and control arms: a) symptom treatment (Palliative Care Domain index); b) symptom control (Symptom Management at the End of Life in Dementia scale, Neuropsychiatric Inventory Questionnaire); c) post-acute use of community palliative care or hospice; and d) new nursing home transitions. *Patients in intervention vs. control arms will have better symptom treatment (H2a) and symptom control (H2b); increased use of community palliative care or hospice (H2c); and fewer new nursing home transitions at 60 days post-discharge (H2d).*

**Aim 3:** To compare caregiver-centered secondary outcomes between intervention and control arms: a) communication about prognosis and goals of care; b) shared decision-making; and c) caregiver distress (Family Distress in Advanced Dementia scale and Zarit scale). *Caregivers in intervention vs control arms will more often have documented communication about prognosis and goals of care (H3a); report more shared decision-making about hospitalization and treatments (H3b); and report less caregiver distress at 60-days post-discharge (H3c).*

### 9.2 SAMPLE SIZE DETERMINATION

Based on prior ADRD research, we project 15% dropouts (death, withdrawal) equally distributed between groups; caregiver data collection is completed after deaths as in our prior ADRD

research. Total sample size for analysis of 60-day follow-up outcomes is thus n=360. All statistical tests will be 2-tailed with an overall 0.05 significance level for pre-specified analyses. Statistical power is based on a 2-sided alpha of 0.05 significant tests and using standard deviation estimates from our pilot study (**Table 3**).

Power calculations assume a “best guess” 15% dropout (death, withdrawal) rate based on prior ADRD research (n=180 per group at 60-day follow-up) and a “worst case” 25% dropout rate (n=159 per group). These rates consider 9% patient mortality and 92% caregiver retention rate in the pilot. In our pilot data, 0.52 is the lower bound of the 95% CI for the IRR comparing

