## 4 STUDY DESIGN

### 4.1 OVERALL DESIGN

Study design is an RCT conforming to SPIRIT and CONSORT statements for trial methods and protocol. Our approach uses NIA standards for a multi-site efficacy trial (Stage II) of a protocolized behavioral intervention, while incorporating pragmatic features to support sustainability and future dissemination. We will use 1:1 randomization of patient-caregiver dyads with concealed allocation until study assignment. Research will occur at 5 geographically diverse sites of the Palliative Care Research Cooperative (PCRC) network, with study leadership and centralized IRB at UNC. Sites will enroll N=424 dyads of hospitalized patients with late-stage ADRD (GDS 6-7 or GDS 5 with significant co-morbidity) with their family caregivers. Sites will additionally enroll N=50 dyads that identify as Hispanic/Latino. Intervention dyads will receive the ADRD-PC program of i) dementia-specific palliative care, ii) standardized caregiver education, and iii) transitional care. Control dyads will receive publicly available educational material on dementia caregiving. Outcomes will be measured at 30 days (interim) and 60 days post-discharge. The primary outcome will be 60-day hospital transfers, defined as visits to an emergency department or hospitalization (**Aim 1**). Secondary patient-centered outcomes will be symptom treatment, symptom control, use of community palliative care or hospice, and new nursing home transitions (**Aim 2**). Secondary caregiver-centered outcomes will be communication about prognosis and goals of care, shared decision-making about hospitalization and other treatments, and caregiver distress (**Aim 3**). The Principal Investigator

and outcome assessors will be masked; as in most behavioral interventions clinicians and participants cannot be masked to study arm. Analyses will use intention-to-treat, and pre-specified exploratory analyses will examine effects of sex as a biologic variable, race / ethnicity, and GDS stage.

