Analysis to Meet Aim 1: We will compare control and intervention arms on hospital transfers (primary outcome) during 60 days post-discharge. This count outcome is defined as the total number of emergency room visits plus hospital admissions per at-risk patient-days. We will use Poisson regression with empirical 'robust' standard errors allowing for overdispersion to compare the transfer rates between groups. We will use the length of follow-up as the offset variable, which means that patients who have data only from the 30-day interview will be included. The primary analysis will be based on the model with main effects for treatment group, study site, GDS Stage and patient and caregiver sex as biological variables. Evaluation of the treatment effect will be based on a Wald test. The covariate-adjusted treatment effect will be quantified as an incidence rate ratio (IRR) with a 95% confidence interval. Considering that over 60% of patients in the pilot study did not have any hospital transfers, we will conduct a sensitivity analysis for the treatment effect on 60-day hospital transfers with a marginalized zero-inflated Poisson (MZIP) model, which may modestly increase power. Secondary Poisson and MZIP analyses will compare study arms for 30-day hospital transfer rates. An exploratory analysis will be conducted to examine interactions of treatment group with study site, sex, race / ethnicity and GDS Stage, respectively, on 60-day hospital transfers. While the proposed study is powered to detect whether or not ADRD-PC is effective, a much larger study would be needed to have adequate power to detect differences by sex or GDS Stage and would be justifiable only after the completion of this initial trial. An interaction model will be used if an omnibus test for interactions is statistically significant at the 0.05 level. A second exploratory analysis will evaluate a dose-response effect of the intervention on the hospital transfer rate. A dose for patients receiving the intervention is defined as the number of key intervention components used in fidelity monitoring (range 0 to 4 with 0 for controls). The dose effect is the incremental benefit of adding a single component; its rescaling gives the per-protocol effect of the full intervention.

---

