#### 9.4.3 ANALYSIS OF THE SECONDARY ENDPOINT(S)

**Aim 2:** To compare patient-centered secondary outcomes between intervention and control arms: a) symptom treatment (Palliative Care Domain index); b) symptom control (Symptom Management at the End of Life in Dementia scale, Neuropsychiatric Inventory Questionnaire); c) post-acute use of palliative care or hospice; and d) transition to nursing home care.

Analysis to Meet Aim 2: We will compare study arms during 60 days post-discharge on the following outcomes:

2.a. Symptom treatment: This ordinal outcome is the summation of presence (=1) or absence (=0) of 10 domains of palliative care. We will treat it as a continuous variable due to a high variation observed in the pilot data. We will use Student's t-test to compare the mean difference between study arms unless violation of assumptions warrants the Mann-Whitney test. We will use a multiple linear regression model with main effects for treatment group, study site, GDS Stage and patient and caregiver sex as a biological variable.

2.b. Symptom control: We will use Symptom Management (SM-EOLD) scale to measure caregiver report of patients' uncontrolled symptom distress and Neuropsychiatric Inventory Questionnaire (NPI-Q) to measure caregiver report of patients' neuropsychiatric symptom distress. Linear mixed models with random intercepts for patients will be used with a time indicator (30 vs 60 days follow-up) with the above main effects.

2.c. Use of post-acute palliative care or hospice: This outcome will be defined by whether patients ever use hospice or outpatient palliative care during the time from discharge to 60 days follow-up. We will compare the proportions using Pearson's chi-square test. Logistic regression will be used for multivariable modeling with the same main effects as in Aim 2.a. Final estimates will be reported as covariate-adjusted odds ratios.

2.d. Transition to nursing home care: This outcome will be defined by whether patients transition to nursing home care during the time from discharge to 60 days follow-up. We will compare proportions using Pearson's chi-square test. Logistic regression will be used for multivariable modeling with the same main effects as in Aim 1. Final estimates will be reported as covariate-adjusted odds ratios.

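### Section 9.2 claims an overall 0.05 level across the pre-specified analyses, but the plan delivers it for the primary outcome only

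*Combined protocol and SAP*

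**What the plan says.** Section 9.2 (Sample Size Determination) sets the error level: "All statistical tests will be 2-tailed with an overall 0.05 significance level for pre-specified analyses". The next sentence gives the level behind the power table: "Statistical power is based on a 2-sided alpha of 0.05 significant tests".

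Section 9.1 names one primary hypothesis (H1) and directional secondary hypotheses H2a to H3c. Under Aim 2 these cover "a) symptom treatment (Palliative Care Domain index); b) symptom control (Symptom Management at the End of Life in Dementia scale, Neuropsychiatric Inventory Questionnaire"), then palliative care or hospice use and nursing home transition. Under Aim 3 they cover communication, shared decision-making and caregiver distress.

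Section 9.4.2 gives the primary outcome one deciding test: "Evaluation of the treatment effect will be based on a Wald test". The zero-inflated model is labelled a sensitivity analysis.

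Section 9.4.3 gives most secondary outcomes an unadjusted test and also a model. For 2a: "We will use Student's t-test to compare the mean difference between study arms unless violation of assumptions warrants the Mann-Whitney test", followed by a multiple linear regression. For 3c it assigns a t-test to the hypothesis and then linear mixed models to test 30-day and 60-day effects jointly. For 2c, 2d, 3a and 3b it gives chi-square tests plus logistic regression, with adjusted odds ratios as the reported estimates.

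Section 9.4 has no hierarchy, gatekeeping, Holm, Bonferroni or false discovery rate rule, and does not say that secondary p-values are nominal.

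**The concern.** An overall level for a set of analyses ordinarily means that the chance of any false positive in that set is held at 5%. Nothing in the plan does this for the secondary outcomes. A reader who relies on Section 9.2 could take a secondary result with p just below 0.05 as protected when it is not.

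A second, smaller problem is that some hypotheses have two tests with no rule on which decides. If the two disagree, the choice is made after the data are seen.

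**Working it through.** **Counting the outcomes (Sections 3, 9.1, 9.4.3).**
- Primary: 60-day hospital transfers.
- Aim 2, five: Palliative Care Domain Index, SM-EOLD, NPI-Q, palliative care or hospice use, nursing home transition.
- Aim 3, six: prognosis discussion, goals-of-care discussion, decision-making about hospitalization, decision-making about treatments, Family Distress in Advanced Dementia (FDAD), Zarit.

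That makes 11 secondary outcomes and 12 in all. NPI-Q and Zarit have no row in Table 3, and the 3c analysis text names only FDAD, so the count is best called about 11. The 30-day comparisons and exploratory interactions are not counted.

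**Which alpha does Table 3 use?** Allocation is 1:1 (Section 4.1). Section 9.2 gives "n=180 per group at 60-day follow-up" with 15% dropout, and 159 per group with 25%. For means, power = Φ(d / (SD × √(2/n)) − z). For the Palliative Care Domain Index at n = 180: 0.5 / (1.7 × √(2/180)) = 2.790. With z = 1.960 this gives Φ(0.830) = 0.797, against 0.80 stated. With z = 2.838 (alpha 0.05/11) it gives Φ(−0.048) = 0.481. Proportions use the usual normal approximation. Results at n = 180 / 159:

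| Outcome and difference | Table 3 | alpha 0.05 | alpha 0.05/11 |
|---|---|---|---|
| PC Domain Index, 0.5 (SD 1.7) | 0.80 / 0.75 | 0.797 / 0.746 | 0.481 / 0.415 |
| SM-EOLD, 2.3 (SD 7.8) | 0.80 / 0.75 | 0.799 / 0.748 | 0.484 / 0.417 |
| FDAD, 0.15 (SD 0.5) | 0.81 / 0.76 | 0.812 / 0.763 | 0.503 / 0.435 |
| Hospice use, 3% to 11% | 0.85 / 0.80 | 0.848 / 0.801 | 0.555 / 0.483 |
| Goals of care, 25% to 39% | 0.82 / 0.77 | 0.815 / 0.766 | 0.504 / 0.435 |
| Decisions on hospitalization, 0% to 4% | 0.78 / 0.73 | 0.776 / 0.724 | 0.449 / 0.385 |
| Decisions on treatments, 6% to 15% | 0.80 / 0.75 | 0.798 / 0.747 | 0.479 / 0.412 |

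Prognosis discussion has the same inputs and result as hospice use. The nursing home row (0.82 / 0.78) reproduces as a rise from 33% to 48% (0.829 / 0.780). A fall to 18%, the direction of H2d, gives 0.907 / 0.870. Neither fits 0.05/11 (0.525 / 0.454 and 0.668 / 0.593). The primary Poisson row at a difference of 0.25 gives 0.956 to 0.961 at n = 180, against 0.96 stated, and 0.931 to 0.939 at n = 159, against 0.95. The overdispersed rows fit only with an assumed variance factor of about 1.7, which the documents do not state, so they cannot show which alpha was used. The secondary rows were thus computed at an unsplit 0.05 per outcome.

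**Family-wise error when each outcome is tested at 0.05, all nulls true.**
- Independent tests: 1 − 0.95^11 = 0.431 for the secondaries; 1 − 0.95^12 = 0.460 for all 12.
- Equal correlation (assumed; simulated normal statistics) of 0.3 / 0.5 / 0.7: about 0.38 / 0.30 / 0.22 for 11 outcomes and 0.40 / 0.32 / 0.23 for 12.

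**Two tests on one outcome.** If either p-value below 0.05 were accepted, that outcome's error would rise from 5% to about 5.9% at an assumed correlation of 0.98 between the tests, and to 7.8% at 0.80.

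**The case against.** The strongest reply is that the family-wise reading rests on one word. The following sentence describes a per-test level, Table 3 follows it, and the outcomes are called secondary throughout. *Overall* may be loose drafting. That is plausible, but the sentence still says something the design does not do.

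A reader might go further and infer that the trial has no type I error control. The documents do not support that. There is one primary outcome with one named Wald test in a specified model, and testing secondaries does not inflate it. Nor is testing secondaries at a nominal level a fault in itself; the fault is describing it as an overall level.

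A reader might also take 43% or 46% as the expected error rate. Those figures need independence and every null true. The pilot in Section 4.2 makes a global null implausible (Palliative Care Domain Index 7.6 vs 2.7; prognosis discussion 90% vs 3%).

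Finally, it is too strong to say that the plan never indicates which result counts. Eight secondary outcomes have both an unadjusted test and a model; for six of them (2c, 2d, and two measures each under 3a and 3b) adjusted odds ratios are named as the reported estimate. What stands is that chi-square remains the stated test for those outcomes, and that 2a and 3c have no deciding test.

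**Conclusion.** The sentence in Section 9.2 is wrong as written and should be corrected. The overall two-sided 0.05 level is a property of the primary analysis only. Across the 11 secondaries the chance of at least one false positive is up to 43% (independence, all nulls true). For all 12 outcomes it is 46%, or about 23% to 40% at assumed correlations of 0.7 to 0.3. That each secondary is tested at 0.05 is inferred from the power sentence, the reproduced Table 3 rows and the absence of any adjustment; Section 9.4 does not restate alpha by outcome. The missing deciding test is a real but smaller gap.

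**What to change.** Preferred change to Section 9.2: state that the two-sided 0.05 level applies to the primary outcome, and that secondary outcomes are tested at a nominal 0.05 with no family-wise control and reported as supportive. This costs only wording; secondary claims become slightly weaker.

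If an overall claim is kept, use one procedure covering all outcomes, for example the primary first and then Holm over all secondaries together. Holm run separately within Aim 2 and Aim 3 would not do: two families at 0.05 allow 1 − 0.95² = 9.8%, and three with the primary 1 − 0.95³ = 14.3%, if independent. The Table 3 secondary power must then be restated. At the first Holm step (0.05/11) it falls from about 0.80 to about 0.48 at the smaller Palliative Care Domain Index and SM-EOLD differences. At the larger, pilot-size differences it stays at or above 0.95, except for FDAD. Putting the primary first also means no confirmatory secondary claim if the primary fails.

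In either case, name one deciding test for each hypothesis that has two, above all 3c and 2a. If a model is chosen, fix its covariates in advance, because Section 9.4.1 lets them enter or leave by change in effect. For binary outcomes with control rates near zero (0% and 3% in Table 3; 3% of 180 is about 5 events), keep a test that is valid with sparse cells. Ordinary adjusted logistic regression alone may fail there through separation.

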**Table 3: Power for Comparing Intervention and Control Arms Based upon the Study Design**

| Aim       | Measure                                   | Control | SD  | Difference | Power, 15% dropout | Power, 25% dropout |
|-----------|---|---------|-----|------------|--------------------|--------------------|
| 1  | 60-day hospital transfers (Poisson rate)  | 0.53    | --  | 0.25, 0.2  | 0.96, 0.82         | 0.95, 0.79         |
|           | 60-day hospital transfers (overdispersed) | 0.53    | --  | 0.25, 0.2  | 0.81, 0.60         | 0.76, 0.55         |
| 2a | PC Domain Index (0-10)                    | 2.7     | 1.7 | 5, 0.5     | >0.99, 0.80        | >0.99, 0.75        |
| 2b | 60-day hospice use (%)                    | 3%      | --  | 22%,8%     | >0.99, 0.85        | >0.99,0.80         |
| 2c | Symptom distress (SM-EOLD)                | 36.4    | 7.8 | 4, 2.3     | >0.99, 0.80        | >0.99, 0.75        |
| 2d | Transition to nursing home care (%)       | 33%     | --  | 30%,15%    | >0.99, 0.82        | >0.99, 0.78        |
| 3a | Discussion of dementia prognosis          | 3%      | --  | 87%, 8%    | >0.99, 0.85        | >0.99, 0.80        |
| 3a | Discussion of goals of care (%)           | 25%     | --  | 65%,14%    | >0.99, 0.82        | >0.99, 0.77        |
| 3b | Decision-making about hospitalization     | 0%      | --  | 13%, 4%    | >0.99, 0.78        | >0.99, 0.73        |
| 3b | Decision-making about treatments          | 6%      | --  | 47%, 9%    | >0.99, 0.80        | >0.99, 0.75        |
| 3c | Family Distress in Advanced Dementia      | 2.4     | 0.5 | 0.15, 0.1  | 0.81, 0.47         | 0.76, 0.43         |

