### **Electronic Health Record Review:**

1. Symptom assessment and management plans during hospitalization-
  - a. Palliative Care Domain Index Items
2. Documented discussion of dementia prognosis
3. Documented discussion decision-making for goals of care
4. New nursing home transfers
5. Return to acute care – ED or Hospital readmissions within 60 days and up to 3 reasons for return

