#### 9.3 POPULATIONS FOR ANALYSES

N/A

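### Table 3, row 2d: the stated power of 0.82/0.78 is not the power for the reduction in nursing home transitions that H2d predicts, which is 0.91/0.87

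*Combined protocol and SAP*

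**What the plan says.** Table 3 in section 9.2 lists "Transition to nursing home care" as row 2d. It shows a control rate of 33%, two differences printed without a sign (30 and 15 points), and power for each. Power for 30 points is above 0.99 in both dropout columns. Power for 15 points is 0.82 at 15% dropout and 0.78 at 25% dropout.

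Section 9.2 sets a two-sided alpha of 0.05. It gives the group sizes as "n=180 per group at 60-day follow-up" for 15% dropout and 159 per group for 25% dropout. For the first case it adds: "Total sample size for analysis of 60-day follow-up outcomes is thus n=360".

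The direction comes from section 9.1, where the hypothesis for the intervention arm is "fewer new nursing home transitions at 60 days post-discharge (H2d".

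Section 9.4.3, item 2.d, names Pearson's chi-square test and defines the endpoint as follows: "This outcome will be defined by whether patients transition to nursing home care during the time from discharge to 60 days follow-up". The section headed "POPULATIONS FOR ANALYSES" (9.3) contains only N/A.

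**The concern.** The power to detect a difference between two proportions depends on the direction of the change as well as its size, because the variance depends on the rates. A move from 33% down to 18% has smaller variance than a move from 33% up to 48%, so the same 15 points are easier to detect. Row 2d is the only binary row of Table 3 in which the hypothesis predicts a decrease. It is also the only binary row whose stated power differs from the power for the hypothesised direction.

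What is at stake is the accuracy of a published power statement for one secondary endpoint. A reader who takes the row at face value will believe that the trial is about 9 points less powerful for a 15-point reduction than it is at the stated group sizes.

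**Working it through.** **Inputs.** Control rate 33% and difference 15 points (Table 3, row 2d); n = 180 and 159 per group and two-sided alpha 0.05 (section 9.2); 1:1 allocation (section 4.1); Pearson chi-square (section 9.4.3, item 2.d); direction downward (section 9.1, H2d).

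**Formula.** Two-proportion z-test, equivalent to Pearson chi-square, with pooled variance under the null:

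power = Φ{ (|p1 − p2| − 1.96·s0) / s1 }

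with s0 = √[2·p̄(1 − p̄)/n], s1 = √[(p1(1 − p1) + p2(1 − p2))/n] and p̄ = (p1 + p2)/2.

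**Step 1: the plan's own figure.** Add the 15 points, giving 33% vs 48% and p̄ = 0.405.
- n = 180: s0 = 0.0517, s1 = 0.0511; (0.15 − 0.1014)/0.0511 = 0.950; power 0.829.
- n = 159: s0 = 0.0551, s1 = 0.0544; (0.15 − 0.1079)/0.0544 = 0.774; power 0.780.

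The plan states 0.82 and 0.78. The second value matches. The first is within 0.01, although 0.829 rounds to 0.83.

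**Step 2: the hypothesised direction.** Subtract the 15 points, giving 33% vs 18% and p̄ = 0.255.
- n = 180: s0 = 0.0459, s1 = 0.0453; (0.15 − 0.0900)/0.0453 = 1.325; power 0.907.
- n = 159: s0 = 0.0489, s1 = 0.0482; (0.15 − 0.0958)/0.0482 = 1.125; power 0.870.

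**Step 3: does the choice of formula explain the gap?** For 33% vs 18% at n = 180/159:

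| Method | Power |
|---|---|
| Pooled | 0.907 / 0.870 |
| Unpooled | 0.912 / 0.876 |
| Arcsine | 0.909 / 0.873 |
| Exact Pearson | 0.911 / 0.873 |
| Continuity-corrected | 0.885 / 0.840 |
| Fisher exact | 0.888 / 0.843 |

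None comes within 0.02 of 0.82/0.78.

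**Step 4: the other binary rows.** The pooled formula, with the difference added as those hypotheses require, gives:

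| Row | Rates | Computed | Stated |
|---|---|---|---|
| "60-day hospice use" and prognosis discussion | 3% vs 11% | 0.848 / 0.801 | 0.85 / 0.80 |
| Goals-of-care discussion | 25% vs 39% | 0.815 / 0.766 | 0.82 / 0.77 |
| Decision about hospitalization | 0% vs 4% | 0.776 / 0.724 | 0.78 / 0.73 |
| Decision about treatments | 6% vs 15% | 0.798 / 0.747 | 0.80 / 0.75 |

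All agree within 0.01, so this is evidently the plan's method or one very close to it.

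**Step 5: what the stated power corresponds to.** With a 33% control rate, 0.82 at n = 180 belongs to a reduction of 13.3 points, and 0.78 at n = 159 to one of 13.4 points. Power of 0.80 is reached at reductions of 13.0 and 13.8 points. The 30-point scenario exceeds 0.99 in either direction at both group sizes.

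**The case against.** The strongest reply is that the difference is printed unsigned, and that the printed inputs do give 0.83/0.78 when the 15 points are added. That stands. A reader might infer that the stated power follows from no reading of the row, and that would be too strong. What is established is narrower: the figures fit the direction opposite to H2d.

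It is also fair that unsigned differences are a convention of the table. The symptom-distress and family-distress rows are unsigned reductions too. For a comparison of means with a common SD, however, the sign does not affect power. For a proportion it does.

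A second stronger reading is that the row may overstate power, because patients already in a nursing home cannot make a new transition and would leave the denominator. Section 9.1 and the EHR list in section 8.1 ("New nursing home transfers") do say new, while row 2d and item 2.d do not. For 33% vs 18%, about 137 to 140 and 124 to 126 patients per arm would give 0.82 and 0.78 after rounding. Those numbers are obtained only by working back from the answer. The documents give no share of prior residents and no reduced n, and section 9.2 applies n=360 to the 60-day outcomes. Purely as an assumption, with the control rate held at 33%, excluding 10% to 30% of patients would give power from 0.88/0.83 down to 0.78/0.73. Nothing in the documents selects a value in that range. The sentence just before Table 3 breaks off in the text available, so a lost note on the denominator cannot be ruled out.

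Finally, the table's practical message, roughly 80% power or better for a 15-point reduction, remains true at the stated n. That argues for low severity, not for leaving the row as it is.

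**Conclusion.** The point holds as a minor error. For the reduction that H2d predicts, 33% vs 18%, power at the stated 180 and 159 per group is 0.91 and 0.87, against the 0.82 and 0.78 given. The row understates power by about 9 points in each column, so the error is conservative.

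The most likely explanation is that the difference was added to the control rate, as is correct in the other binary rows. The documents do not confirm it, and the near miss at n = 180 (0.829 against 0.82) leaves some doubt.

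The conclusion rests on the group sizes and alpha in section 9.2, the 33% control rate, the direction in section 9.1, and all patients counting in the denominator, as item 2.d reads. It concerns one secondary endpoint. N=424, the planned tests and the 30-point scenario are unaffected.

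**What to change.** Restate row 2d of Table 3 as 33% vs 18%, with power 0.91 at n=180 and 0.87 at n=159 per group. Show the larger scenario as 33% vs 3%, with power still above 0.99.

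If the sponsor in fact used a smaller at-risk group for new transitions, state that number per arm in sections 9.2 and 9.3 and in item 2.d of 9.4.3, and give the power for 33% vs 18% at that number instead.

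The cost is one table row and, in the second case, a sentence on the denominator. Sample size, tests and data collection do not change.
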